3 STUDY DESIGN

3.1 Description of Study Design

This is a phase 2 multicenter, randomized, placebo-controlled, double-blind, parallel-group, 36-month clinical trial to evaluate the effectiveness and safety of intervention with a 12-month course of HCQ to prevent the future onset of clinically-apparent RA (see definition in Section 2.1, *Primary Objective*). At screening, study subjects will be without IA but will be at high-risk for developing future RA within the trial period as indicated by elevated anti-CCP3 antibodies that are ≥ 40 units (that is a level ≥ 2 times the normal cut-off of ≥ 20 units). Two hundred eligible subjects will be randomized in a 1:1 ratio to receive either self-administered HCQ or placebo.

Subjects will provide informed consent prior to any Pre-Screening or Screening procedures. Subjects who are found to be eligible after the screening evaluation will return for a Baseline/Randomization visit within 30 days of the initial screening visit. Subject eligibility will be confirmed prior to randomization. Eligible subjects will be randomized to receive either 200 - 400 mg of HCQ or placebo daily for 12 months based upon ideal body weight (IBW) at Screening. The weight-based dosing regimen for the study is outlined in Section 5.2, *Dosage Regimen*.

Subjects will return to the study site for planned evaluations at Weeks 6, 12, 24, 36, and 52 (End of Treatment), and Months 18, 24, 30, and 36 (End of Study). During these study visits, subjects will have a joint exam and a physical examination. Study personnel will record the subject's interval medical history, assess AEs, and collect samples for safety and mechanistic assessments (see Tables 6.1 and 6.2, *Schedule of Events*, for specific assessment schedule). Information on demographics (including socio-economic status and education), and other factors that may influence autoimmunity (e.g. tobacco exposure, hormonal status and exposures) will also be collected.

Site coordinators will also call subjects at Week 18, 30, and 42, and at Month 15, 21, 27, and 33 to answer subject questions, update contact information, and to assess AEs/reactions, study drug dosing and pregnancy status (during the treatment period), and joint symptoms. If a subject indicates that he/she is experiencing joint symptoms suggestive of RA (that include new or worsening joint pain, stiffness or swelling since the prior study visit) or symptoms suggestive of an AE, the subject will be asked to return to the study site for evaluation via an unscheduled visit as soon as possible. Visits and assessments for subjects who develop RA, IA with erosions, or who become pregnant prior to the Month 36 visit will be different from subjects who never develop these conditions. Details of these assessments may be found in protocol sections 6.5.9, *Evaluations Triggered by a Swollen Joint*, 6.5.10, *Procedures for Subjects Diagnosed with*

⁴ Risk factors include but are not limited to age, sex, genetic factors, socio-economic status, education, tobacco exposure, medications and medical hormone use, and dietary factors.

Inflammatory Arthritis or Rheumatoid Arthritis by an Outside Physician, and 6.5.11, Special Considerations for Pregnant Subjects.

Subject use of non-immunomodulatory agents such as acetaminophen, non-steroidal anti-inflammatory drugs (NSAIDS), and herbal supplements are allowed. DMARDs, systemic corticosteroids, and biologic therapies are prohibited during study participation as outlined in Section 5.6, *Prohibited Medications*.

After completing the screening period, the expected duration of study participation for each subject is 36 months.

The enrollment period is projected to be approximately 24 months from the opening of the first 75% of study sites.

3.1.1 Stratification, Randomization, and Blinding

Subjects will be randomized in a 1:1 ratio to either HCQ or placebo. As some study sites may only randomize a few subjects, an adaptive randomization procedure based on Pocock and Simon[165] minimization concepts will be used to increase the likelihood of balance between treatment arms on key factors associated with progression to clinically-apparent RA. The key factors will include smoker status (smoker vs. non-smoker), study site, and method of recruitment (i.e. FDR, general population, or clinic screening. For additional detail on recruitment strategies, see Section 4.3, *Strategies for Recruitment and Retention*).

To maintain the study blind, the appearance of the study treatments, HCQ and placebo, and their packaging will be identical. Clinical staff will be blinded to the treatment assignments until completion of the study with the exception of an unblinded pharmacist. In addition, clinical staff members, including the investigators, will not have access to any mechanistic data, and mechanistic laboratory staff will not have access to any clinical results until completion of the study.

An individual's treatment assignment will only be unblinded if the subject experiences a suspected adverse reaction that is serious and unexpected (see Section 7.2.2, *Adverse Reaction and Suspected Adverse Reaction* and Section 7.2.3, *Unexpected Adverse Reaction*) or other protocol-specific event(s) determined by DAIT/NIAID to warrant unblinding.

3.1.1.1 Subject Completion and Replacement

A subject is considered to have completed the study if he/she has completed the Month 36 visit. Subjects who withdraw from the study prior to receiving drug will not be counted towards the target accrual of 200 subjects. Eligible subjects receiving at least one dose of study drug will count towards target accrual.

3.2 Description of Primary Endpoint

The primary efficacy endpoint is the development of clinically-apparent RA by 36 months, where clinically-apparent RA is defined in Section 2.1, *Primary Objective*.

3.3 Description of Secondary Endpoints

3.3.1 Secondary Efficacy Endpoints

1. Time to development of clinically-apparent RA as defined in Section 2.1, *Primary Objective*.
2. Time to development of a swollen joint(s) that is (are) consistent with RA-like synovitis.
3. Development of clinically-apparent RA by 12 months, where clinically-apparent RA is defined in Section 2.1, *Primary Objective*.
4. Development of a swollen joint(s) that is (are) consistent with RA-like synovitis by 12 months, where synovitis is determined by joint exam.
5. Trends in disease activity during the treatment period (i.e. Baseline through Week 52) will be evaluated over time using multiple indices:
 - Physician assessed tender joint count
 - Physician assessed swollen joint count
 - DAS28-CRP score
 - Clinical Disease Activity Index (CDAI)
 - Routine Assessment of Patient Index Data 3 (RAPID-3)
6. Trends in disease activity during the post-treatment follow-up period (Week 52 through Month 36) will be evaluated over time using multiple indices (as noted in above).
7. Trends in patient self-reported evaluations of joint pain, stiffness and swelling will be evaluated over the treatment period (i.e. Baseline through Week 52). The following endpoints are of interest:
 - Total number of painful joints
 - Total number of stiff joints
 - Total number of swollen joints
 - Number of painful joints in the hands, in the wrists, in the feet
 - Number of stiff joints in the hands, in the wrists, in the feet
 - Number of swollen joints in the hands , in the wrists, in the feet
8. Trends in patient self-reported evaluations of joint pain, stiffness and swelling will be evaluated over the post-treatment follow-up period (Week 52 through Month 36). See specific endpoints noted above.
9. Trends in patient-reported outcomes (PRO) for physical, mental and social health (collected via NIH Patient-reported Outcomes Measurement Information System (PROMIS) instrument Profile 29 v2.0) will be evaluated over the treatment period (i.e. Baseline through Week 52).

10. Trends in PRO for physical, mental and social health will be evaluated over the post-treatment follow-up period (Week 52 through Month 36).

3.3.2 Secondary Safety Endpoints

Safety for individual subjects will be monitored by assessing AEs and serious adverse events (SAEs) and measuring hematology and clinical chemistry parameters at scheduled visits and unscheduled visits (as needed) throughout the trial. Safety events that might cause discontinuation of treatment for an individual or trigger a safety review of the study by the Data and Safety Monitoring Board (DSMB) are described in Sections 5.8.1, *Study Treatment Discontinuation* and 5.8.3, *Safety Stopping Guidance*, respectively.

Safety analyses are described more fully in Section 8.3.2, *Safety Analysis*, but the following endpoint is of particular interest in describing the safety profile of HCQ for prevention of RA:

- The proportion of subjects in each arm experiencing a Grade 3 or higher AE according to the National Cancer Institute-Common Terminology Criteria for Adverse Events (NCI-CTCAE) system.

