7.3.2 Collection Period

AEs of NCI-CTCAE Grade 2 and above will be collected from the time the subject signs the main clinical trial informed consent until he/she initiates study intervention or until he/she is determined to be ineligible to receive study intervention, if the investigator determines that the AE is related to a study-mandated procedure, treatment, or change in treatment.

Regardless of whether the above is applicable, for all participants, AEs of NCI-CTCAE Grade 2 and above will be collected from the time of initiation of study intervention (i.e., the administration of the first dose of study drug (HCQ/placebo), as defined in Section 6.5.3, *Baseline/Randomization Visit*), until Month 18 or until 30 days after he/she prematurely withdraws (without withdrawing consent) or is withdrawn from the study.

Serious adverse events will be collected throughout the duration of the subject’s participation in the study.

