7.3.4 Recording Adverse Events

AEs of NCI-CTCAE Grade 2 and above will be recorded from the time the subject signs the main clinical trial informed consent until he/she initiates study intervention or until he/she is determined to be ineligible to receive study intervention, if the investigator determines that the AE is related to a study-mandated procedure, treatment, or change in treatment.

From the initiation of study therapy through Month 18 or until 30 days after the subject prematurely withdraws or is withdrawn from the study, the investigator will record and grade AEs of NCI-CTCAE Grade 2 and above on the appropriate AE electronic case report form (AE eCRF) regardless of their severity or relation to study medication or study procedure.

Once recorded, an AE will be followed until it resolves with or without sequelae, or until the end of study participation, or until 30 days after the subject prematurely withdraws (without withdrawing consent)/or is withdrawn from the study, whichever occurs first.

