7.4 Grading and Attribution of Adverse Events

7.4.1 Grading Criteria

The study site will grade the severity of AEs experienced by the study subjects according to the criteria set forth in the NCI-CTCAE v4.0. This document (referred to herein as the NCI-CTCAE manual) provides a common language to describe levels of severity, to analyze and interpret data, and to articulate the clinical significance of all AEs. The NCI- CTCAE has been reviewed by the Protocol Chair(s) and has been deemed appropriate for the subject population to be studied in this protocol.

AEs will be graded on a scale from 1 to 5 according to the following standards in the NCI-CTCAE manual:

Grade 1 = mild adverse event, not recorded.

Grade 2 = moderate adverse event.

Grade 3 = severe and undesirable adverse event.

Grade 4 = life-threatening or disabling adverse event.

Grade 5 = death.

If NCI-CTCAE criteria are defined for grading an abnormal value or result from a clinical or laboratory evaluation (including, but not limited to, a radiograph, an ultrasound, or an electrocardiogram), then a treatment-emergent AE is defined as an increase in grade from Baseline (Day 0) or from the last post-Baseline value that doesn't meet grading criteria. Changes in grade from screening to Baseline (Day 0) will also be recorded as outlined in Section 7.3.2, *Collection Period*. If a specific event or result from a given clinical or laboratory evaluation is not included in the NCI-CTCAE manual, then an abnormal result would be considered an AE if changes in therapy or monitoring are implemented.

AEs that are related to disease activity will be graded according to the plan outlined above. However, an increase in disease activity leading to an AE should also be reflected in standard measures of disease activity measured at study visits.

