8.3.2 Safety Analysis

All safety analyses will be performed using the Safety Population.

The frequency of AEs will be summarized by system organ class, preferred term, severity (grade), and relationship to study treatment. Relationship to study treatment will be categorized as either treatment related (possibly, probably, or definitely related to study medication) or unrelated (unlikely related or unrelated). Similar analyses will be performed for SAEs. To account for differential duration of study participation among subjects, the summaries will also include the event rate (i.e. number of events per person-time) in addition to the number and percent of events and subjects experiencing events.

For each key safety endpoint defined in Section 3.3.2, *Secondary Safety Endpoints* the proportion of subjects experiencing at least one event in each treatment group will be reported and the treatment groups compared based on Fisher's Exact Test.

Laboratory parameters will be summarized both overall and by treatment group using appropriate descriptive statistics. For each lab parameter, the number and percent of subjects that have an increase, decrease, or no change from Baseline to Week 52, Month 24, and 36 will be displayed for each treatment group and pooled across treatment arms. For parameters with an explicit NCI-CTCAE grading criterion, change from baseline will be indicated by a change in grade. For parameters that do not have an explicit NCI-CTCAE grading criterion, observed values will be categorized as 'high' (defined as $>\text{ULN}$), 'normal' (defined as \geq lower limit of normal (LLN) and \leq ULN), or 'low' (defined as $<\text{LLN}$). Then, a change from baseline will be indicated as a change in category.

Laboratory data will also be plotted to show patterns over time. Summary statistics including 25th percentile, median, and 75th percentile will be plotted for each visit by treatment group. Lines connecting individual subject results from subjects with Grade 2 or higher values will be overlaid on each figure. For lab results that are not gradable, results from subjects with values outside of 2 *ULN or 0.5*LLN will be overlaid.

All safety comparisons and associated p-values are considered exploratory, not as formal tests of hypothesis. As such, no adjustments will be made for multiple comparisons and all p-values must be interpreted cautiously.

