9.3. Adverse Events

All AEs will be classified by system organ class (SOC) and preferred term, according to a standardized thesaurus (Medical Dictionary for Regulatory Activities [MedDRA] version 23.0). The severity of AEs will be classified using the National Cancer Institute's (NCI's) Common Toxicity Criteria for Adverse Events (CTCAE) version 4.0. Each AE is entered on the electronic case report form (CRF) once at the highest severity. As such, no additional data manipulation is needed to identify events.

AEs will be collected starting at consent for Grade 2 or higher AEs related to a study-mandated procedure, treatment, or change in treatment, and will be collected starting from the first dose of study treatment through Month 18 or until 30 days after the participant prematurely terminates from the study, whichever occurs first. SAEs are collected for participants throughout the duration of their participation in the study. Treatment-emergent AEs will be identified as those with an onset date on or after the first dose of study medication. If the start of the AE in relation to the start of study medication cannot be established (e.g., the start date for the AE is missing), then the AE will be considered treatment-emergent. If an abnormal laboratory finding is reported as an AE on the first day of study drug (Day 1), these events will not be considered treatment emergent since these assessments occur prior to treatment initiation. All data tabulations will be of only treatment-emergent events while non-treatment-emergent AEs will be included in the listing of all AEs.

The frequency of AEs will be summarized by system organ class, preferred term, severity (grade), and relationship to study treatment. Relationship to study treatment, as determined by masked investigators, will be categorized as either treatment related (possibly, probably, or definitely related to study medication) or unrelated (unlikely related or unrelated). Similar analyses will be performed for SAEs. To account for differential duration of study participation among participants, the summaries will also include the event rate (i.e., number of events per person-time) in addition to the number and percent of events and participants experiencing events.

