For the secondary safety endpoint of the proportion of participants in each arm experiencing a Grade 3 or higher AE according to the National Cancer Institute-Common Terminology Criteria for Adverse Events (NCI-CTCAE) system, the proportion of participants experiencing at least one event in each treatment group will be reported and the treatment groups compared based on Fisher's Exact Test.

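### The Grade 3 or higher AE comparison counts RA's own adverse events, so a real RA benefit would dilute a small HCQ harm; one supplementary table would separate the two

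*Protocol*

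**What the plan says.** Protocol 3.3.2 singles out one safety endpoint: "The proportion of subjects in each arm experiencing a Grade 3 or higher AE". SAP 9.3 carries it forward and names the method for comparing the arms: "the proportion of participants experiencing at least one event in each treatment group will be reported and the treatment groups compared based on Fisher's Exact".

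Three provisions bring RA events into this count:

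- Protocol 7.4.1: "AEs that are related to disease activity will be graded according to the plan outlined above".
- Protocol 7.3.4: AEs of Grade 2 and above are recorded "regardless of their severity or relation to study medication or study procedure".
- SAP 9.3: "Treatment-emergent AEs will be identified as those with an onset date on or after the first dose of study medication". The definition has no end date tied to the last dose or to an RA diagnosis.

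Under protocol 7.3.2, non-serious AEs of Grade 2 and above are collected "until Month 18 or until 30 days after he/she prematurely withdraws". SAE collection goes on for as long as the subject takes part.

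Protocol 8.3.2 calls all safety comparisons exploratory. Both documents also tabulate AEs by system organ class, preferred term, grade and relationship, with person-time rates.

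**The concern.** In this trial, becoming ill with the target disease is both the efficacy outcome and a source of adverse events. Any RA prevention by HCQ removes some Grade 3 or higher events from the HCQ arm. A drug harm adds events to the same arm. The all-cause proportion nets the two.

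Secondary objective 1 asks about the safety of 12 months of HCQ in people who do not yet have disease. Similar all-cause proportions could mean that HCQ causes no extra severe events. They could also mean that a small excess of drug-related events was balanced by fewer RA-related ones. The planned endpoint alone cannot tell these apart.

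**Working it through.** **Inputs from the documents.** Protocol 8.1 assumes RA in 50% on placebo and 25% on HCQ at 3 years, with exponential times, hazards of 0.231 and 0.096 per year and a hazard ratio of 2.4. It plans 100 per arm. The interim SAP (5.2.2.1) reports 144 randomized, about 72 per arm.

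**Reproducing the plan's figures.** Hazards are −ln(0.50)/3 = 0.2310 and −ln(0.75)/3 = 0.0959, a ratio of 2.41. Exact enumeration of the logit Wald test at 80 per arm, without censoring, gives 91.1% power (plan: 90%). The plan states no expected rate or power for the safety endpoint.

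**Step 1: RA risk by arm.** R(t) = 1 − exp(−hazard × t).

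| Time | Placebo | HCQ | Gap (points) |
|---|---|---|---|
| Month 12 | 20.6% | 9.1% | 11.5 |
| Month 18 | 29.3% | 13.4% | 15.9 |
| Month 36 | 50% | 25% | 25 |

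Month 18 is the relevant row, because non-serious AE collection ends then.

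**Step 2: RA-driven gap in the endpoint.** Let q be the share of RA cases with an RA-related Grade 3 or higher AE. The documents do not give q; 5–20% is an assumption. Before overlap with other AEs, the extra on placebo is q × 15.9 points:

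- q = 5%: 0.8 points
- q = 10%: 1.6 points
- q = 20%: 3.2 points

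Over the first 12 months alone, q × 11.5 gives 0.6–2.3 points.

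**Step 3: size of harm that could be offset.** Let b be the non-RA Grade 3 or higher risk on placebo and h the true HCQ excess. Treat RA-related and other AEs as independent, and write R_P and R_H for the Month 18 RA risks:

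- placebo = 1 − (1 − b)(1 − q·R_P)
- HCQ = 1 − (1 − b − h)(1 − q·R_H)

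The two are equal when h = (1 − b)·q·(R_P − R_H)/(1 − q·R_H). With b = 10% (assumed), this gives h = 0.7, 1.5 and 2.9 points for q = 5%, 10% and 20%.

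Solving instead for q gives q = h/[(1 − b)R_P − (1 − b − h)R_H]. At b = 10%, full offset needs q = 14% for a 2-point harm, 33% for 5 points and 64% for 10 points. For b from 5% to 20% the ranges are 13–15%, 32–37% and 61–71%.

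**Step 4: effect on the test.** This is the power of the two-sided 0.05 Fisher test to find HCQ worse, with b = 10% and h = 10 points (both assumed).

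| q | Expected gap (points) | 100 per arm | 72 per arm |
|---|---|---|---|
| 0 (no RA events) | 10.0 | 44% | 32% |
| 5% | 9.2 | 36% | 26% |
| 10% | 8.4 | 30% | 21% |
| 20% | 6.9 | 19% | 14% |

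For a 3-point harm with no RA events at all, power is already only 5–8% at 100 per arm and 4–5% at 72 per arm, for b from 5% to 20%.

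**The case against.** Much of the case on the other side stands.

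- **The premise is a design-stage one.** SAP 5.4 records that the DSMB recommended stopping because the interim results showed evidence of futility. The RA difference in the data may be small or absent, and the tilt would shrink with it.
- **The share q has no source.** Repeated joint examinations, phone calls and referral at diagnosis suggest that RA would often be caught early, which points to the low end of the range.
- **The lost sensitivity is small in absolute terms.** Harms small enough to be fully offset could hardly be detected at these sample sizes anyway, and the p-values are exploratory.
- **Other displays help.** Preferred-term and relationship tables and the AE listings let a reader see RA-type events. The DSMB trigger in protocol 5.8.3 counts only HCQ-arm SAEs at least possibly related to HCQ, so placebo RA events cannot mask it.

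The existing tables do not, however, give the proportion of participants with at least one non-RA Grade 3 or higher event. One participant can appear under several terms, so the rows cannot be added. The relationship table asks about attribution to drug, which is a different question.

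A reader might also infer a 5-point effect on SAEs by Month 36, from 25 points × 20%. The documents do not support that. Protocol 7.2.4 defines seriousness separately from grade, so a share assumed for Grade 3 or higher events does not carry over to SAEs, and no SAE share is given.

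**Conclusion.** The point holds as a modest, conditional bias. The text is clear that RA-related events enter the one tested AE endpoint. Under the design hazards they add about 0.8–3.2 points to placebo by Month 18 if q is 5–20%. This dilutes a true HCQ excess and could offset one of about 1–3 points.

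A reader might go further and conclude that a real HCQ harm of any size could be cancelled out. The figures do not support this: at 10% background, a 10-point harm would need about 64% of RA cases to have an RA-related Grade 3 or higher event.

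The estimate rests on constant hazards with the design effect acting from randomization, on independence of RA-related and other AEs, and on assumed values of q and background risk. It is worth acting on because the remedy is cheap and leaves the safety contrast interpretable whatever the RA difference proves to be.

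**What to change.** Keep the all-cause comparison as planned. Add to SAP 9.3 one supplementary table by arm: participants with at least one Grade 3 or higher AE, excluding manifestations of RA or inflammatory arthritis.

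- **Term list.** Use a narrow MedDRA preferred-term list of arthritis and synovitis terms. Leave out general musculoskeletal, myopathy and fatigue terms: protocol 1.4.2.2 lists myopathy and lassitude among possible HCQ effects, so a broad list could remove real toxicity.
- **Masking.** SAP 5.4 says that assignments are unmasked before database lock. The list should therefore be set from dictionary terms by reviewers without access to arm-level AE data.
- **Status.** Present it beside the all-cause result. Making it the sole answer to objective 1 would be a trade-off, because any exclusion list can misclassify events.
- **Stated limits.** AEs from RA drugs started after diagnosis remain in this table. Any display limited to time before RA diagnosis needs person-time rates, because under the design assumption it would shorten placebo exposure more.

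The cost is one extra table and a brief medical review of the term list. No new data are needed.
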